6.2 Recording of data

Web Based Data Capture (WBDC) will be used for data collection on the observations, tests and assessments specified in the protocol and query handling. The investigator will ensure that data are recorded on the eCRFs as specified in the protocol and in accordance with the instructions provided. These instructions provide guidance for the recording of study data in the eCRF including how to change data incorrectly recorded.

The investigator ensures the accuracy, completeness, and timeliness of the data recorded and for the provision of answers to data queries according to the Clinical Study Agreement or applicable information.

The investigator will sign the completed eCRFs. A copy of the completed Case Report Forms will be archived at the study site.

For details of data and study management see Appendix E of this Clinical Study Protocol.

6.3 Safety procedures

6.3.1 Enrollment and screening

The principal investigator (PI) will:

- 1. Obtain signed informed consent from the potential patient before any study specific procedures are performed.
- 2. Assign potential patient a unique enrollment number, beginning with "E#".
- 3. Determine patient eligibility. See Sections 4.1 and 4.2.

As patients are screened for the study, they must be allocated an enrollment code (E-code). The E-code is a 7-digit number made up of the centre number and the patient number within that particular centre (eg, the first patient screened at centre number 0001 would be assigned the E-code E0001001, the second patient screened would be E0001002 and so on). This number is the patient's unique identifier and is used to identify the patient on the eCRFs.

If a patient withdraws from participation in the study, then his/her enrollment code cannot be reused.

Demographic data and other characteristics will be recorded and will include date of birth or age, gender, race and/or ethnicity according to local regulations, smoking history.

A standard medical, medication and surgical history will be obtained with review of the selection criteria with the patient.

Each patient will undergo screening (see Study Plan Table 2) during the 28 days prior to admission to confirm eligibility (see Sections 4.1 and 4.2). Tumour assessments and other clinical data obtained as standard of care prior to consent may be used for the study provided

the assessments fall within the protocol specified period prior to the first dose of study treatment.

Prior to discharge from each in-patient and clinic visit, the Investigator or their deputy will be responsible for reviewing all available data including vital signs and ECG tracings.

6.3.2 Physical examination

A complete physical examination will be performed at the visits as indicated in the Study Plan (Table 2).

Performance status will be assessed at screening, prior to the first dose of study treatment, at the beginning of each cycle, and at discontinuation according to WHO criteria as follows:

0 = Fully active, able to carry out all pre-disease activities without restrictions

1 = Restricted in physically strenuous activity but ambulatory and able to carry out work of a light or sedentary nature e.g., light housework, office work

2 = Ambulatory and capable of self-care, but unable to carry out any work activities. Up and about more than 50% of waking hours

3 = Capable of only limited self-care, confined to bed or chair more than 50% of waking hours

4 = Completely disabled, cannot carry on self-care, totally confined to bed or chair

6.3.3 Vital signs

6.3.3.1 Pulse and blood pressure

Supine blood pressure and pulse rate will be measured after 10 minutes rest. Assessments will be performed pre-dose, at the visits as shown in the Study Plan (see Table 2) and on occurrence of any cardiac AE. Additionally at the discretion of the investigator if clinically indicated.

Any changes in vital signs should be recorded as an AE if applicable.

6.3.3.2 Weight and height

Weight will be performed at screening and then Day 1 of each cycle as well as the Discontinuation Visit.

Height will be assessed at screening only.

6.3.4 ECG

Resting 12-lead ECG

Twelve-lead ECG will be performed at the visit indicated in the Study Plan (Table 2).

Twelve-lead ECGs will be recorded at the following times:

- Screening
- On Day 1 of Cycle 0
 - Pre-dose only
- Day 1 of Cycle 1 and each subsequent cycle
 - Pre-dose only
- On occurrence of any cardiac AE
- Discontinuation visit

The timing and number of ECGs may be altered depending on the emerging PK and safety profile.

Twelve-lead ECGs will be obtained after the patient has been resting semi-supine for at least 10 minutes prior to times indicated. All ECGs should be recorded with the patient in the same physical position. For each time point three ECG recordings should be taken at about 5 minute intervals. A standardised ECG machine should be used and the patient should be examined using the same machine throughout the study if possible.

After paper ECGs have been recorded, the investigator or designated physician will review each of the ECGs and may refer to a local cardiologist if appropriate. A paper copy should be filed in the patient's medical records. If an abnormal ECG finding at screening or baseline is considered to be clinically significant by the investigator, it should be reported as a concurrent condition. For all ECGs details of rhythm, ECG intervals and an overall evaluation will be recorded.

6.3.5 Laboratory safety assessment

Blood and urine samples for determination of clinical chemistry, haematology and urinalysis will be taken at the visits as indicated in the Study Plan (see Table 2). Laboratory tests do not need to be repeated at baseline if the baseline visit is within 7 days of the screening sample.

Blood and urine samples for safety assessment will be collected at the following times:

- Screening
- First dosing day (Day 1 Cycle 0); pre-dose (baseline)
- First day of multiple dosing, Day 1 Cycle 1; pre-dose
- Multiple dosing, Days 8 and 15 of Cycle 1; pre-dose

- On Day 1 of each subsequent cycle; pre-dose
- Discontinuation visit

The date of each collection will be recorded in the appropriate eCRF.

Following review of data from a group of patients the timing of blood samples may be adjusted for subsequent groups of patient. Additional sampling times may be added if indicated by the emerging data.

Laboratory values that meet the criteria for CTCAEv4 grade 3 or have changed significantly from baseline and are considered to be of clinical concern will be repeated/confirmed within 7 days and followed up as appropriate.

Clinical chemistry	Haematology
Serum (S)/Plasma (P)-Albumin	Blood (B)-Haemoglobin
S/P-ALT	B-Leukocyte
S/P-AST	B-Haematocrit
S/P-Alkaline phosphatase	B-Red blood cell (RBC) count
S/P-Bilirubin, total	B-Absolute leukocyte differential count
S/P-Calcium, total	Neutrophils
S/P-Creatinine	Lymphocytes
S/P-Glucose (fasting on PK days only)	Monocytes
S/P-Magnesium	Basophils
S/P-Potassium	Eosinophils
S/P-Sodium	B-Platelet count
S/P-Urea nitrogen	B-Reticulocytes
	Urinalysis
	U-Glucose
	U-Protein
	U-Blood

The following laboratory variables will be measured:

Additionally a urine/serum sample will be collected from all females of child bearing potential at screening, before first dose for a pregnancy test.

NB. In case a subject shows an AST or ALT $\geq 3x$ ULN and total bilirubin $\geq 2x$ ULN please refer to Appendix G 'Actions required in cases of combined increase of aminotransferase and total bilirubin-Hy's Law' for further instructions.

For blood volume see Section 6.6.1.

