5.2 Dose and treatment regimens

AstraZeneca will supply AZD9291 as tablets for oral administration as a single daily dose of 40 mg and 80 mg respectively. At each dispensing visit, sufficient AZD9291 for 21 days treatment, plus overage, will be dispensed.

Patients will be administered a single dose of AZD9291 on Day 1, Cycle 0 at the beginning of Part A period. From Day 2 to Day 6, no treatment will be given, but PK samples will be obtained; on Day 8 (Cycle1, Day1), the patients will be administered AZD9291 on a continuous schedule. Part A treatment will complete at the end of Cycle 4 and treatment in Part B will continue.

Patients may continue receiving AZD9291 until treatment discontinuation criteria are met. Patients may receive AZD 9291 beyond disease progression as long as they are considered to receive clinical benefit continuously judged by the treating physician.

Patients who were started and have remained on treatment at a dose of 40mg for at least 6 months, have shown clinical benefit (as judged by the investigator) and have then developed RECIST confirmed disease progression, and did not experience any treatment – related grade 3 AE when treated at dose of 40mg, may have dose increased to 80mg after agreement in advance between the Investigator and AZ Study Physician. 80mg has been declared to have an acceptable tolerability profile by the Safety Review Committee.

Tablets should be taken whole with water, 240ml being the recommended volume for PK days. AZD9291 can be taken with or without food at the same time each day. Patients will be required to fast (water only) for at least 8 hours prior to the collection of a fasting glucose sample as per the study plan (Table 2).

Doses should be taken approximately 24 hours apart at the same time each day. Doses should not be missed. If a patient misses taking a scheduled dose, within a window of 12 hours, it is acceptable to take the dose. If it is more than 12 hours after the dose time, the missed dose should not be taken, and patients should be instructed to take the next dose at the next scheduled time. If a patient vomits after taking their AZD9291, they should not make up for this dose, but should take the next scheduled dose.

Any change from dosing schedule, dose interruptions, dose reductions should be recorded in the eCRF.

Assessment timings if dosing is interrupted

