6. STUDY PLAN AND COLLECTION OF STUDY VARIABLES

6.1 Study Plan

Table 2Study Plan

Study Plan 40 & 80 mg tablet cohort

	Screening	Sing (7 d	gle dose ay cycl	e /Cycl e)	le O		Mult Cycle	iple I e 1 (2	Dosing/ 1 Day (cycle)	Cycle 2 – Cycle 4 (21 Day Cycle)	Cycle 2 only	Cycle 5 onwards (21 Day cycle)	Discontinuation	28-day Follow-Up	Details in Section
Visit	1	2	3	4	5	5	6	7	8	9	10+					
Day	-28 to -1	D1	D2	D3	D4	D6	D1	D8	D9	D15	D1	D2				
Window (Days)		0	0	0	0	0	0	0	0	0	±7	0	±7	0	±7	
Informed Consent	Х															4
Demography & baseline characteristics	Х															6.3.1
Medical/surgical history	Х															6.3.1
Inclusion/Exclusion Criteria	Х															4
Physical Examination	Х	Х					Х				Х		Х	X		6.3.2
WHO Performance Status	Х	Х					Х				Х		Х	Х		6.3.2
Pregnancy Test (pre- menopausal females only)	X															6.3.5
Ophthalmologic assessment	Х	•	As clinically indicated								6.3.6					
Vital Signs	X	X	Х				X	X	X	X	X	Х	Х	X		6.3.3
Height	X															6.3.3

Weight	Х	Х					Х				Х		Х	X		6.3.3
ClinicalChemistry/Hae matology/Urinalysis	X	X					Х	Х		X	X		X	X		6.3.5
ECG	Х	Х					Х				Х		Х	X		6.3.4
Echo/MUGA	X	-				1	2 week	dy(±1	week)	relativ	ve to first d	ose				6.3.7
PK blood samples (including metabolites)		X	X	X	X	X	X	X	X	X	X (Cycle 2 only)	X				6.5.1
RECIST assessments	X ^(b)						•	Every	y 6 we	eks(±1	week) ^(c)					6.7.1
Dispense Study Medication		X					X				X		X			5
Dose with AZD9291		Х					•	-		Da	aily dosing					5
Concomitant Medication	•			·	·									· · ·	•	4.3.1
Adverse Events ^(d,e)	•														►	6.4

(a) If assessments were performed within 7 days prior to the first dose of study treatment and the patient meets the eligibility criteria, these assessments do not need to be repeated during visit 2.

(b) This assessment does not need to be repeated if it is performed within 28 days prior to the start of study treatment, unless the investigator has a reason to believe that there has been a change in the patient's tumour burden. If imaging is repeated before the start of study treatment, the most recent assessment would then be recorded as the screening tumour assessment.

(c) RECIST assessments should be performed every 6 weeks (\pm 7 days) from visit 6(C1D1).

(d) Following AZD9291 discontinuation, SAEs considered related to study procedures should continue to be collected

(e) Continued to collect unresolved AEs post 28-day Follow-up visit (if applicable).

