The maximum plasma concentration (C_{max}), the C_{max} at steady state ($C_{ss max}$), the time of maximum concentration (t_{max}) and the t_{max} at steady state ($t_{ss max}$) will be determined by inspection of the concentration-time profiles. Where possible the terminal elimination rate constant (λ_{z}) will be calculated by log-linear regression of the terminal portion of the concentration-time profiles where there are sufficient data and the terminal half-life $(t_{\nu_{\lambda}z})$ will be calculated as $\ln 2/\lambda_z$. The area under the concentration-time curve up to the last quantifiable sample (AUC_(0-t)) and the area under the concentration-time curve up to 24 hours (AUC₍₀₋₂₄₎) will be calculated using the linear up log down trapezoidal rule. Where appropriate, the AUC(0-t) will be extrapolated to infinity using λz to obtain AUC. The area under the concentration-time curve across the dosing interval, AUCss will be calculated using the linear up log down trapezoidal rule. The apparent clearance (CL/F following the single dose and CLss/F following multiple dosing) will be determined from the ratio of dose/AUC or dose/AUCss. The volume of distribution (Vss/F or Vz/F) will be determined from the mean residence time (MRT) x CL/F and/or the accumulation ratio (RAC) will be calculated as the ratio of the AUC(0-24) on Cycle 2 Day 1 and Cycle 0 Day 1. The time dependency of the pharmacokinetics on multiple dosing will be assessed by the calculation of the ratio of AUC(0 -24) Cycle 2 day 1/AUC Cycle 0 Day 1.

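### The only fasting rule follows the glucose test, which can be waived on Cycle 0 Day 1, so meals can enter the accumulation and time-dependency ratios and the glucose baseline

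*Protocol*

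**What the plan says.** **Food and dosing.** Section 5.2 states "AZD9291 can be taken with or without food at the same time each day". It recommends a water volume for PK days but sets no food condition for them. The only fast is in the same paragraph: "Patients will be required to fast (water only) for at least 8 hours prior to the collection of a fasting glucose sample".

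**When glucose is fasting.** The laboratory table in Section 6.3.5 lists "S/P-Glucose (fasting on PK days only".

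**The waiver.** Section 6.3.5 lists the laboratory baseline as "First dosing day (Day 1 Cycle 0); pre-dose (baseline" and also says "Laboratory tests do not need to be repeated at baseline if the baseline visit is within 7 days of the screening sample". Footnote (a) to Table 2 agrees: if the assessments were done in the 7 days before the first dose and the patient is eligible, "these assessments do not need to be repeated during visit 2". Visit 2 is Cycle 0 Day 1. No such allowance is given for Cycle 1 Day 8 or Cycle 2 Day 1, where pre-dose laboratory samples are scheduled.

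**The ratios.** Under Section 7.4 the accumulation ratio "will be calculated as the ratio of the AUC(0-24) on Cycle 2 Day 1 and Cycle 0 Day 1". Time dependency divides the Cycle 2 Day 1 AUC(0-24) by the single-dose AUC. Section 7.1 lists both among the primary endpoints.

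**The concern.** Whether a patient must fast before the single dose depends on how recently the screening bloods were taken, not on any PK consideration. Before the Cycle 2 Day 1 dose, with which the single dose is compared, the fast always applies. Both ratios are within-patient, so their value lies in holding everything else constant between the two days. A prandial difference would pass straight into them and could read as more or less accumulation, or as clearance changing over time.

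Later analysis could not repair this. Section 6.5.1 records dose and sample times, but the protocol asks for no meal times. A dose taken after food is permitted, so it is not a deviation that the PK analysis set in Table 5 would exclude. With about 12 patients per cohort, a few discordant patients carry weight.

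The second issue is glucose. Because it is fasting only on PK days, a patient's series combines two kinds of value. Section 6.3.5 calls for repeat testing when a value has changed significantly from baseline and is of clinical concern, and Section 7.7 grades laboratory values by CTCAE. Meal-related shifts could therefore be read as drug effects.

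**Working it through.** **1. Reproduce the planned sample counts.** Section 6.6.1 gives 9 clinical chemistry samples and 39 PK samples per patient, assuming 4 cycles on average.

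- Chemistry, from Table 2 and Section 6.3.5: screening, C0D1, C1D1, C1D8, C1D15, C2D1, C3D1, C4D1, discontinuation = 9. This matches.
- PK, from Table 4: 15 (Cycle 0) + 14 (Cycle 1) + 10 (Cycle 2) = 39. This matches.

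**2. Mark which chemistry samples must be fasting.** These are the laboratory visits that are also PK days.

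| | Fasting required | No fasting requirement |
|---|---|---|
| Waiver not used | C0D1, C1D1, C1D8, C1D15, C2D1 (5) | Screening, C3D1, C4D1, discontinuation (4) |
| Waiver used | C1D1, C1D8, C1D15, C2D1 (4) | Screening, C3D1, C4D1, discontinuation (4) |

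With the waiver, 9 − 1 = 8 samples remain and the glucose baseline is the screening value, which need not be fasting. The mixing itself does not depend on the waiver: it is 5 against 4 without it and 4 against 4 with it.

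**3. Compare the two days in the ratios for a patient using the waiver.**

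| | Cycle 0 Day 1 (denominator) | Cycle 2 Day 1 (numerator) |
|---|---|---|
| Glucose sample due | No | Yes |
| Fast required before the draw | No | Yes, 8 hours |
| Food rule between draw and dose, or after dose | None | None |

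The last row matters. The fast ends at the pre-dose draw, so even the Cycle 2 Day 1 dose is only implied to be fasted.

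**4. Size under assumptions.** Let *f* be the fed/fasted AUC ratio and *w* the share of patients fed on Cycle 0 Day 1 and fasted on Cycle 2 Day 1. The document gives neither. In a discordant patient the denominator is multiplied by *f*, so the ratio is multiplied by 1/*f*. Averaging on the log scale, the geometric mean ratio is multiplied by *f*^(−*w*). The same factor applies to time dependency if *f* acts equally on AUC(0-24) and AUC to infinity.

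| *f* | *w* = 0.25 | *w* = 0.5 | *w* = 1 (also one affected patient) |
|---|---|---|---|
| 1.3 | 0.94 | 0.88 | 0.77 |
| 1.2 | 0.96 | 0.91 | 0.83 |
| 1.1 | 0.98 | 0.95 | 0.91 |
| 1.0 | 1.00 | 1.00 | 1.00 |
| 0.9 | 1.03 | 1.05 | 1.11 |
| 0.8 | 1.06 | 1.12 | 1.25 |
| 0.7 | 1.09 | 1.20 | 1.43 |

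For example, *f* = 1.2 and *w* = 0.5 gives 1.2^(−0.5) = 0.913, a ratio about 9% too low. *f* = 0.8 and *w* = 0.5 gives 0.8^(−0.5) = 1.118, about 12% too high. If food raises exposure, accumulation is understated; if food lowers it, accumulation is overstated.

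The formula treats the whole numerator as fasted. That is a simplification, because exposure on Cycle 2 Day 1 also contains drug from earlier daily doses, which may be taken regardless of meals.

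**The case against.** The strongest reply is that the PK part needs a food effect, and the document gives none. Permitting dosing regardless of meals suggests that the sponsor expects little effect, and supporting data may lie in the Investigator's Brochure, which is not shown. This stands: the bias may be nil, and the table above illustrates rather than estimates.

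Second, a reader might infer that waiver patients are profiled fed and then fasted, so that the ratios are biased. The document does not support that. A waived test removes a requirement to fast; it does not make anyone eat. Discordance needs screening bloods in the last 7 days of a window running from Day −28 to Day −1, a site that uses an optional waiver, and a patient who eats. The default plan takes the sample, and the count of 9 includes it.

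Third, a reader might expect glucose to fall in Cycles 1 and 2 and rise from Cycle 3. That does not follow either, because the other samples may still be taken fasting. The mixing also comes mainly from restricting fasting to PK days; the waiver adds only the baseline problem. Splitting glucose tables by fasting status could be left to an analysis plan.

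Fourth, the ratios are descriptive, safety data are not formally analysed, and no decision rule uses either. Meal times might be covered in eCRF instructions or the Laboratory Manual, which are not shown.

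These points limit the size and certainty of the problem. They do not remove the mismatch: the protocol imposes different fasting requirements on the two days that its primary ratios compare, and an analysis plan cannot recover a food state that was neither controlled nor recorded.

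**Conclusion.** The point holds as a conditional one. For patients using the waiver, the single-dose day has no fasting requirement and the Cycle 2 Day 1 profile day does, so a prandial difference can enter the accumulation and time-dependency ratios. The factor is *f*^(−*w*). At *w* = 0.5 it is 0.95, 0.91 or 0.88 for *f* = 1.1, 1.2 or 1.3, and 1.05, 1.12 or 1.20 for *f* = 0.9, 0.8 or 0.7. At *f* = 1 there is no bias. Both *f* and *w* are assumptions, so the document does not show that the ratios are biased, only that they are not protected.

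The glucose point needs no assumption about how food affects drug exposure. Values at screening, from Cycle 3 and at discontinuation need not be fasting, while those in Cycle 1 and on Cycle 2 Day 1 must be, and the waiver can put the baseline in the first group. Change from baseline and CTCAE grade can therefore reflect meals rather than drug.

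This is an avoidable confounder worth removing cheaply, not a flaw that undermines the study.

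**What to change.** **Section 5.2 and Table 2.** Reconcile the food, fasting and waiver passages so that one consistent prandial condition, before and after dosing, applies on Cycle 0 Day 1, Cycle 1 Day 8 and Cycle 2 Day 1, whether or not laboratory tests are due. Which condition to use is for the sponsor to decide. Record the times of the last meal before and the first meal after the dose on those days.

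**Section 6.3.5 and Table 2 footnote (a).** Exempt Cycle 0 Day 1 glucose from the 7-day waiver, so that baseline is collected under the same rule as the Cycle 1 and Cycle 2 Day 1 values. Present fasting glucose separately from values with no fasting requirement.

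**Cost.** A few sentences, two eCRF fields, and one extra glucose test and fasting morning for patients who would have used the waiver. Dosing on other days is untouched, so carry-over from doses taken regardless of meals would remain in the Cycle 2 Day 1 profile.

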4.1 Inclusion criteria

For inclusion in the study, patients must fulfill all of the following criteria:

- 1. Provision of signed and dated, written informed consent prior to any study specific procedures, sampling and analyses
- 2. Aged at least 18 years
- 3. Histological or cytological confirmation diagnosis of NSCLC
- 4. Locally advanced or metastatic NSCLC, not amenable to curative surgery or radiotherapy

- 5. Radiological documentation of disease progression while on a previous continuous treatment with an approved EGFR-TKI eg, gefitinib, erlotinib, icotinib or afatinib. In addition other lines of therapy may have been given.
 - Documented EGFR mutation (at any time since the initial diagnosis of NSCLC) known to be associated with EGFR TKI sensitivity (including G719X, exon 19 deletion, L858R, L861Q).
- 6. World Health Organisation (WHO) performance status 0-1 with no deterioration over the previous 2 weeks and a minimum life expectancy of 12 weeks
- 7. At least one lesion, not previously irradiated that can be accurately measured at baseline as ≥10 mm in the longest diameter (except lymph nodes which must have short axis ≥15 mm) with computerised tomography (CT) or magnetic resonance imaging (MRI) which is suitable for accurate repeated measurements.
- 8. Females should be using adequate contraceptive measures (see Section 4.3), should not be breast feeding and must have a negative pregnancy test prior to start of dosing if of child-bearing potential or must have evidence of non-child-bearing potential by fulfilling one of the following criteria at screening:
 - Post-menopausal defined as aged more than 50 years and amenorrhoeic for at least 12 months following cessation of all exogenous hormonal treatments
 - Women below 50 years old would be consider postmenopausal if they have been amenorrheic for 12 months or more following cessation of exogenous hormonal treatments and with LH and FSH levels in the post-menopausal range for the institution
 - Documentation of irreversible surgical sterilisation by hysterectomy, bilateral oophorectomy or bilateral salpingectomy but not tubal ligation
- 9. Male patients should be willing to use barrier contraception ie, condoms

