 - Mean resting corrected QT interval (QTc) >470 msec obtained from 3 electrocardiograms (ECGs), using the screening clinic ECG machine derived QTc value
 - Any clinically important abnormalities in rhythm, conduction or morphology of resting ECG eg, complete left bundle branch block, third degree heart block, second degree heart block, PR interval >250 msec

- Any factors that increase the risk of QTc prolongation or risk of arrhythmic events such as heart failure, hypokalaemia, congenital long QT syndrome, family history of long QT syndrome or unexplained sudden death under 40 years of age in first degree relatives or any concomitant medication known to prolong the QT interval
- 6. Past medical history of interstitial lung disease, drug-induced interstitial lung disease, radiation pneumonitis which required steroid treatment, or any evidence of clinically active interstitial lung disease
- 7. Inadequate bone marrow reserve or organs function as demonstrated by any of the following laboratory values:
 - Absolute neutrophil count $<1.5 \times 10^9/L$
 - Platelet count $<100 \times 10^9/L$
 - Haemoglobin <90 g/L
 - Alanine aminotransferase >2.5 times the upper limit of normal (ULN) if no demonstrable liver metastases or >5 times ULN in the presence of liver metastases
 - Aspartate aminotransferase >2.5 times ULN if no demonstrable liver metastases or >5 times ULN in the presence of liver metastases
 - Total bilirubin >1.5 times ULN if no liver metastases or >3 times ULN in the presence of documented Gilbert's Syndrome (unconjugated hyperbilirubinaemia) or liver metastases
 - Creatinine >1.5 times ULN concurrent with creatinine clearance <50 ml/min (measured or calculated by Cockcroft and Gault equation); confirmation of creatinine clearance is only required when creatinine is >1.5 times ULN
- 8. Refractory nausea and vomiting, chronic gastrointestinal diseases, inability to swallow the formulated product or previous significant bowel resection that would preclude adequate absorption of AZD9291
- 9. History of hypersensitivity to active or inactive excipients of AZD9291 or drugs with a similar chemical structure or class to AZD9291
- 10. Women who are breast feeding
- 11. Involvement in the planning and conduct of the study (applies to AstraZeneca staff or staff at the study site)

12. Judgment by the investigator that the patient should not participate in the study if the patient is unlikely to comply with study procedures, restrictions and requirements

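### The only scheduled pregnancy test falls in a 28-day screening window with no closer limit, so a first dose may rest on a negative result up to 28 days old

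*Protocol*

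**What the plan says.** Four places in the protocol fix the timing of the test.

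- **Section 6.3.5:** "Additionally a urine/serum sample will be collected from all females of child bearing potential at screening, before first dose for a pregnancy test".
- **Table 2 (Section 6.1):** the pregnancy-test row has one mark, under Screening (Day -28 to -1), and none at Visit 2 (Cycle 0 Day 1) or later.
- **Section 4.1, inclusion 8:** such a woman "must have a negative pregnancy test prior to start of dosing if of child-bearing potential". No number of days is given.
- **Section 6.3.1:** "Each patient will undergo screening (see Study Plan Table 2) during the 28 days prior to admission to confirm eligibility". The whole window therefore counts for eligibility.

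The blood-volume table in Section 6.6.1 allows for one serum β-HCG sample of 4 mL.

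A 7-day limit exists for other assessments. Section 6.3.5 states: "Laboratory tests do not need to be repeated at baseline if the baseline visit is within 7 days of the screening sample". Footnote (a) to Table 2 has a similar condition, "If assessments were performed within 7 days prior to the first dose of study treatment and the patient meets the eligibility criteria", and then waives the repeat at Visit 2.

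Pregnancy is not itself an exclusion criterion. Exclusion 10 reads only: "Women who are breast feeding".

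**The concern.** A negative test taken early in the window says little about a woman's status on the day of her first dose. A conception shortly before the test may not yet be detectable, and one after the test cannot show in it. The schedule does not look again before AZD9291 is given.

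The protocol treats exposure in pregnancy as something to stop. Section 8.3.1 calls for immediate discontinuation if a patient becomes pregnant, Section 5.5 lists pregnancy among the reasons for stopping treatment, and Section 4.3 continues contraception for 3 months after treatment ends. The first dose is the point at which exposure could be prevented rather than followed up, and the safeguard there can be four weeks old. What is at stake is patient and fetal safety. No pharmacokinetic, safety-summary or response result depends on it.

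**Working it through.** **1. Is there one test or two?** The wording in Section 6.3.5 names screening and also the time before first dose, which could be read as two occasions. Two other places show one.

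- Table 2 has a single mark.
- The Section 6.6.1 total works only with one β-HCG sample: 9 × 5 + 9 × 2 + 39 × 2 + 1 × 4 = 45 + 18 + 78 + 4 = 145 mL, the protocol's own figure.

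That table does count repeats where they are planned. The 9 safety samples match screening, Cycle 0 Day 1, Cycle 1 Day 1, Cycle 1 Days 8 and 15, Day 1 of Cycles 2 to 4, and discontinuation: 1 + 1 + 1 + 2 + 3 + 1 = 9. A second pregnancy test would have appeared in the same way.

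**2. Age of the test at first dose, as written.** The first dose is on Day 1 and there is no Day 0.

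- Test on Day -1: 1 day old.
- Test on Day -28: 28 days old.

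The range is 1 to 28 days.

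**3. Does another clause shorten this?**

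- *Section 4* requires every criterion to be met when treatment starts. Criterion 8 asks for a negative test before dosing, and any earlier negative test in the window meets it.
- *The 7-day rules* in Section 6.3.5 and footnote (a) excuse a repeat that would otherwise be due at baseline or Visit 2. No pregnancy test is due then, so there is nothing to excuse and the limit does not reach it.
- *Contraception* (inclusion 8 and Section 4.3) reduces the chance of conception but detects nothing. The Section 4.3 obligation starts at screening, so it does not cover a conception just before the test.
- *Extra sampling times* are permitted by Section 6.3.5 if emerging data call for them, but none is required.

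None of these closes the gap.

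**4. With a 7-day limit.**

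| | As written | With the change |
|---|---|---|
| Maximum test age at first dose | 28 days | 7 days (0 if repeated on Cycle 0 Day 1) |
| Reduction in the maximum | – | 28 − 7 = 21 days |
| Screening days on which a test would need a repeat | 0 of 28 | 21 of 28 (Day -28 to -8) |
| Screening days on which it would not | 28 of 28 | 7 of 28 (Day -7 to -1) |
| Estimated blood volume if the repeat uses serum | 145 mL | 145 + 4 = 149 mL (4/145 = 2.8%) |

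These are calendar days, not a measure of risk.

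**The case against.** The strongest reply is that nothing here is inconsistent. Table 2, Section 6.3.5, inclusion 8 and the blood-volume table agree, and the protocol nowhere calls a test from the screening window inadequate. Seven days is not a general rule either: echocardiogram/MUGA, ophthalmology and imaging have no such limit. That is correct, so 7 days should be read as a proposal and not as a standard the protocol has broken.

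A second reply is that the risk is already reduced. Inclusion 8 and Section 4.3 ask for contraception, with a partner's condom added to hormonal methods, and Section 8.3.1 covers stopping, reporting and follow-up. A woman known to be pregnant by Day 1 could not reasonably be dosed on an old negative result, and a site may choose to test late in the window. All of this stands, and it narrows the gap to unsuspected pregnancy. But it permits a recent test without requiring one, and the measures in Section 8.3.1 act only after exposure.

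A third reply is that no harm has been quantified and that a very early conception could be missed even with a recent test. Both are true. They limit how strongly the change can be urged, but they do not justify keeping the older test when the alternative costs so little.

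One caution concerns footnote (a): in the text available, no row of Table 2 visibly carries its marker, so its reach is inferred from its wording. The single mark in the pregnancy-test row makes that inference a safe one.

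**Conclusion.** The concern holds. As written, a woman of child-bearing potential may take her first dose on a negative pregnancy test up to 28 days old and be fully compliant. It is a design choice that should be improved, not an error or a contradiction.

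The conclusion rests on reading the protocol as scheduling one test, which Table 2 and the blood-volume total support. The absolute risk cannot be given, because the protocol does not state how many women of child-bearing potential are expected among the approximately 24 patients. Both that number and the risk may be small. The case for change is that the possible harm is serious and the remedy is nearly free.

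**What to change.** In inclusion 8, Table 2 and Section 6.3.5, require a negative urine or serum pregnancy test within 7 days before the first dose (Cycle 0 Day 1). If the screening test is older than that, repeat it pre-dose at Visit 2.

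In the document this means one phrase in inclusion 8, one mark with a footnote in Table 2 and one phrase in Section 6.3.5. If serum may be used for the repeat, the β-HCG line in Section 6.6.1 should allow for a second 4 mL sample.

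The burden is at most one extra test per woman, at a visit where blood and urine are normally taken, and none if the single screening test is timed on Day -7 to -1. The downsides are that extra test and the remaining chance of missing a very early conception.
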